## 8.2. Statistical Analyses and Data Management

### 8.2.1 Implementation and Effectiveness Outcomes Analyses (Aim 1)

We will conduct intent-to-treat comparisons between arms, using a generalized linear regression model with an identity link and Gaussian error distribution to compare means (e.g., fidelity scores) or an identity link and binomial error distribution to compare proportions (e.g., ART uptake). For patient-level outcomes (e.g. ART uptake), the design effect introduced by clinic-level randomization will be addressed using a robust variance estimate.

Data for all aims will be managed at the UNC-Vietnam. Each site will undergo explicit training in data quality. All data sources, including electronic surveys, paper forms, and audio-recordings will be monitored for quality and completeness. Data queries will be made promptly to the sites, typically within one week. The central data team head will have group quarterly calls with site data representatives to address any ongoing data issues. Specific sites will have calls as needed.

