#### **5.1.4 Randomization**

We obtained a complete list of the 136 HIV test sites in Vietnam, including the number of persons tested per month, positivity rates, and proportion of PWID. These data have been used to identify 42 proposed test sites for inclusion in this implementation study.

Test sites will be stratified by region and size, then randomized to either arm at a 1:1 ratio (21 sites per trial arm). Randomization will be blocked within strata to ensure equal distribution by arm.

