## 8. STATISTICAL CONSIDERATIONS

### 8.1. Power and Sample Size Considerations

#### 8.1.1 *Implementation Outcomes Sample Size Calculations*

The **primary implementation outcome is fidelity**, based on an index with a score ranging from 0-200 (see Section 7.2). The **unit of analysis is test site** (n=42 test sites total, 21 per arm).

In HPTN 074, the Vietnam site achieved 86%-88% completion of navigation and counseling sessions in the protocol-specified window, and in our counseling studies we consistently achieve 90-95% quality scores on supervisor-rated counseling sessions. **This track record suggests a “best case” upper bound to the fidelity score of ~150** [(100\*0.85 navigation sessions completed \* 0.9 quality) + (100\*0.85 counseling sessions completed \* 0.9 quality) = 76.5+76.5 = 153].

**We expect TA to achieve close to this “best case” upper bound, with  $\geq 80\%$  appointment completion and  $\geq 85\%$  quality scores, or a fidelity score of  $\geq 136$  = (100\*0.8\*0.85 + 100\*0.8\*0.85). We expect IM to achieve lower session completion and lower quality.**

*Using two-tailed tests and  $\alpha=0.05$  and assuming a conservatively large standard deviation of 40, 42 sites will give us 80% power to detect a difference between a fidelity score of 136 in the TA arm and 100.5 in the SA arm.*

A score of 100.5 in the TA arm corresponds to 75% session completion and 67% average quality ratings (100\*0.75\*0.67 + 100\*0.75\*0.67 =100.5).

With a more plausible standard deviation of 28, we would have 80% power to detect the difference between a score of 136 in the TA arm and 111 (75% completion,74% quality) in the SA arm. Thus, we have power to detect operationally meaningful differences in session completion and quality scores.

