#### 8.1.2 *Effectiveness Outcomes Sample Size Calculations*

The **primary effectiveness outcome is ART uptake**, measured as a dichotomous variable at the PWID level. After accounting for up to 12% mortality during follow-up, we estimate an available sample of 6200 PWID, with cluster (test site) size ranging from 7-764 PWID (mean≈148). **Loss to follow-up does not affect this outcome**, as patients not retained in clinic will be assumed not to be on ART.

**To calculate the design effect**, we estimate that the intra-cluster correlation coefficient may range from 0.01-0.05, as is typical in clinic-level behavioral interventions, implying a design effect between 2.5 and 8.4.

Using two-tailed tests and  $\alpha=0.05$ , we will have >80% power to detect a difference as small as 10 percentage points (e.g., 70% vs. 60% ART uptake) if the ICC is as large as 0.05, and as small as 6 percentage points (e.g., 70% vs. 64% ART uptake) if the ICC is as small as 0.01. Thus, we are well powered to detect operationally meaningful differences in our primary effectiveness outcome of ART uptake.

For **viral load**, which is based on a sample of  $n=1200$  (~30 per clinic), assuming the same ICC of 0.01-0.05, we will have 80% power to detect differences of 10-14 percentage points in viral suppression between arms (e.g. 40% vs. 30% if  $ICC=0.01$ ; 40% vs. 26% if  $ICC=0.05$ ).

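### The fidelity model omits the region and size strata used to randomize sites, so its interval is wider than necessary if those strata predict fidelity

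*Combined protocol and SAP*

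**What the plan says.** Section 5.1.4 sets out the allocation: "Test sites will be stratified by region and size, then randomized to either arm at a 1:1 ratio (21 sites per trial arm"), and "Randomization will be blocked within strata to ensure equal distribution by arm". The section also says that the sponsor held a list of all candidate sites, "including the number of persons tested per month, positivity rates, and proportion of PWID", so both factors can be fixed for every site before allocation.

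For fidelity, Section 8.1.1 says that the "unit of analysis is test site", which gives 42 values, 21 per arm. It makes two power statements: "assuming a conservatively large standard deviation of 40, 42 sites will give us 80% power to detect a difference" between 136 and 100.5, and "With a more plausible standard deviation of 28, we would have 80% power to detect the difference between a score of 136" and 111.

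Section 8.2.1 is the whole Aim 1 analysis text. It compares the arms "using a generalized linear regression model with an identity link and Gaussian error distribution to compare means (e.g., fidelity scores"). It names no region, size or other covariate. The robust variance that follows is given for patient-level outcomes, to handle clustering, and does not bring in the strata. In Section 8.2.3 the exploratory Aim 3 models do have their terms spelled out: a site measure, an arm indicator and their interaction.

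**The concern.** Blocking on a factor that predicts the outcome makes the arm difference more precise. The analysis reports that gain only if the factor is also in the model. Without it, the between-stratum variation stays in the residual variance. The point estimate is no noisier, but its standard error is overstated, the 95% interval covers more than 95% of the time and the test rejects too rarely.

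Fidelity is a primary outcome with 42 observations and planned power of about 80%, so there is little precision to spare. The stratification factors need no new data collection and should have no missing values. Leaving the terms unstated also leaves a choice open until after the data are seen.

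**Working it through.** **Inputs from the documents.** 21 sites per arm, two-sided alpha 0.05, differences 136 - 100.5 = 35.5 (SD 40) and 136 - 111 = 25 (SD 28), all from Section 8.1.1.

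**Assumed, because the documents do not give them.** R², the share of between-site fidelity variance explained by the strata, is taken as 0 to 0.3. The strata are 3 regions (the regional grouping in Section 5.1.6) or 5 areas (Section 3.1), each with two size groups, making 6 or 10 cells.

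**Step 1: the plan's own figure.** For an unstratified two-sample t test on 40 df, SE = SD × √(2/21).

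- SD 40: SE = 12.34, noncentrality 35.5/12.34 = 2.88, power 80.1%.
- SD 28: SE = 8.64, noncentrality 25/8.64 = 2.89, power 80.6%.

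Both match the stated 80%, so the plan's power calculation uses no strata.

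**Step 2: what blocking does.** With balanced cells the true SE is SD × √(2(1 - R²)/21), while the model without strata still reports about SD × √(2/21). At SD 40 and 6 cells, the 95% half-width is 2.021 × 12.34 = 24.95 without strata (40 df). With cell indicators (35 df, t = 2.030) it is:

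- R² 0.1: 2.030 × 11.71 = 23.77, so the unadjusted interval is 24.95/23.77 = 1.05 times as wide.
- R² 0.2: 2.030 × 11.04 = 22.41, ratio 1.11.
- R² 0.3: 2.030 × 10.33 = 20.97, ratio 1.19.

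**Step 3: simulation.** 10,000 trials per setting (Monte Carlo error about 0.4 points of power), Gaussian site scores, 1:1 within cells, even or odd-sized cells, 6 or 10 cells, SD 40, difference 35.5:

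| R² | Power, arm only | Power, arm + cell indicators | Type I error, arm only | Arm-only interval too wide by |
|---|---|---|---|---|
| 0 | 80-81% | 78-80% | about 5% | none |
| 0.1 | 80-82% | 81-84% | 3.6-4.5% | 1-5% |
| 0.2 | 81-83% | 85-88% | 2.7-3.3% | 8-12% |
| 0.3 | 82-84% | 89-92% | 1.8-2.7% | 16-20% |

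With cell indicators, type I error was 4.5-5.5% throughout. At SD 28 and difference 25 (even cells), power without and with strata was 80 vs 80%, 82 vs 84%, 83 vs 88% and 84 vs 92% at R² 0, 0.1, 0.2 and 0.3. A separate simulation of 6,000 trials per setting agreed: at SD 40, 6 cells and R² 0.3, the true SE was about 10.4, the arm-only model reported about 12.4, and type I error was 1.9%.

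**Step 4: main effects of region and size instead of cell indicators.** At R² 0.3 power was 91-92% if the two effects are additive and 86-88% if they interact. Type I error was 4.5-5.4% (additive) and 3.0-4.8% (interacting).

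**Step 5: the cost if the strata predict nothing** (power, SD 40, difference 35.5). The sparse layouts have one single-site cell out of 6, or three out of 10.

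| Layout | Arm only | Cell indicators | Main effects |
|---|---|---|---|
| 6 even | 80.2% | 79.8% | 80.0% |
| 10 even | 80.0% | 79.5% | 79.9% |
| 6 odd | 80.0% | 79.1% | 79.3% |
| 10 odd | 80.7% | 77.7% | 78.9% |
| 6 sparse | 80.0% | 78.2% | 79.1% |
| 10 sparse | 80.8% | 75.5% | 78.6% |

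**The case against.** Four points can be made for the plan as it stands.

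First, nothing promised is lost. The test stays valid, the stated power is met, and the omission can only make the analysis conservative. That is correct, and it makes this an efficiency point and not an error.

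Second, Section 8.2.1 lists no right-hand-side terms at all and does not rule covariates out, so an unadjusted model is an inference from silence. This stands in part. But the section describes a comparison of means, Section 8.1.1 is powered without strata, and the Aim 3 models show that terms are listed where they are wanted. If adjustment is intended, the text needs to say so.

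Third, R², the number of strata and the cell counts are all assumed, and nothing in the documents shows that R² reaches 0.2. This also stands. At R² 0.1 the gain is only 0-3 points.

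Fourth, cell indicators would not be used with odd or sparse cells, and the main-effects fallback gains less. In 10-cell layouts with interacting effects and R² 0.1, power with main effects was 80.3% against 79.9% unadjusted (odd cells) and 80.3% against 81.1% (sparse cells), which is no gain. At R² 0.2 it gains only about 2 points. With additive effects the sparse case gained about 1 point at R² 0.1 (82.2% vs 81.2%). The cost limit was examined mainly for 6 and 10 cells; a 15-cell layout cost about 1 point with main effects. These results narrow the expected benefit but do not reverse its direction.

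**Conclusion.** The concern holds as a low-cost improvement in efficiency. The allocation is blocked on region and size, and the fidelity model as written does not use them. The arm estimate is unbiased, and type I error is at or below 5%. If the strata explain about 10% of between-site variance, the loss is small. From about 20% it becomes material: power of 81-83% instead of 85-88% at SD 40, and an interval 8-12% too wide. These sizes rest on assumed R², assumed strata and Gaussian site scores, and the upper figures apply to cell indicators. The documents cannot settle where the trial lies in this range. The direction of the effect depends only on the blocking and on the strata being prognostic.

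**What to change.** In Section 8.2.1, state that the fidelity model includes the region and size stratification factors as fixed covariates, with t critical values on the residual degrees of freedom. Define the region and size categories used at randomization. Add a sparse-cell rule: region-by-size cell indicators only if every cell holds an even number of at least four sites; otherwise main effects of region and size. If the sponsor prefers not to adjust, the section should say so in advance.

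The cost is two or three sentences. Residual df fall from 40 to 35 (6 cells) or 31 (10 cells) with cell indicators, or to 37 or 35 with main effects. If the strata predict nothing, the rule keeps the loss to under 1 point with even cells and about 1-2 points otherwise, in the layouts tested.

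This change is for fidelity only. For ART uptake, "with cluster (test site) size ranging from 7-764 PWID", stratum terms should not be added to an uncorrected robust variance; pair them with a small-sample-corrected variance and t critical values. In null simulations with assumed size shapes, ICC 0.05 and z critical values, type I error was 5-11% without strata and 10-18% with them. The choice of variance method for ART uptake is a separate question.

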## **3.3. Inclusion Criteria**

### *PWID participants:*

- 1) HIV infection:
  - Newly diagnosed HIV infection, based on confirmatory test at the test site, and not currently on ART at the time of the study; **or**
  - If previously diagnosed with HIV infection, then not currently on ART at the time of study enrollment (self-reported)
- 2) Age 18 years or older
- 3) Injection drug use within the past 6 months (self-reported at time of screening)
- 4) Willingness to provide informed consent

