#### **5.1.6 Trainings**

- Selection and training of navigators and counselors:

We will train existing HIV test site staff, selected by test site directors, to become systems navigators and psychosocial counselors for SNaP. Test sites will nominate up to three staff per test site as systems navigators and/or counselors. Similar to HPTN 074, the roles of navigators and counselors may be performed by a single person or two distinct persons at the discretion of the test site.

We will conduct regional (north, south, central) trainings for navigators and counselors for all study test sites to ensure that SNaP training is uniform across study arms *prior to* notifying the sites of their SA/TA allocation.

The 2-day, in-person training will be conducted by the centralized training team and rely heavily on the training manual developed for HPTN 074, which will be minimally modified for use at scale. The training will include introduction to motivational interviewing, counseling techniques practices, and a series of guided role play activities, in which real-time feedback will be provided by the training team. Any new navigators or counselors will be trained similarly. Refresher trainings will be held annually.

- **Training on seek strategies:**

At the regional training, implementation teams will provide strategies to reach out to PWID in their catchment area. Strategies will include communicating with needle exchange sites, MAT clinics and other substance use treatment centers (including mandatory 06/07 detoxification centers). The goal is to ensure active referrals of MAT patients to HIV test sites and provide information cards about HIV testing to PWID to distribute in their networks. These strategies were used to effectively “seek” PWID in HPTN 074.

- **Training on implementation strategies for SA and TA:**

During or immediately after the navigator/counselor regional training, a 2-day regional training will be held for all test sites to introduce the project, orient to common implementation barriers and facilitators across sites, and train teams on the SA implementation package. TA implementation teams will subsequently visit each TA site in the region to conduct trainings on site-specific implementation strategies.

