## 5.2. Cluster Randomized Implementation Trial Initiation (Aim 1)

After training completion, sites will implement the SNaP intervention and initiate the trial (Time 0 in Figure 1). SNaP will be implemented as the study rolls out. Specifically, upon trial initiation, trained navigators and counselors will provide SNaP to all accepting PWID testing positive for HIV at the test sites. Time 0 for each site will be the first day that the SNaP intervention is offered at that site.

Each site will consent PWID with a positive confirmatory test at the post-test counseling visit who are willing to allow medical chart review at MAT and ART clinics. Injecting drug use information is collected as part of routine protocol at HIV test sites and will be used to identify eligible participants for the study.

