#### *Selection Bias*

Participation in the study is completely voluntary, and it is possible that those who agree and consent to participate in the study may have different characteristics from those who do not participate. In turn, difference in characteristics may be associated with differences in study results. We will minimize selection bias by assuring confidentiality to all potential participants and addressing any concerns that may arise among potential participants who are hesitant to join the study. We will also track the numbers who decline to participate in the study, providing an estimate of the extent of potential selection bias that may exist.

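### The primary ART-uptake comparison names no covariate, although two different case types are recruited after randomisation by sites not stated to be masked

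*Combined protocol and SAP*

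**What the plan says.** **Model.** Section 8.2.1 plans an intent-to-treat comparison using an "identity link and binomial error distribution to compare proportions (e.g., ART uptake"). On clustering it says that "the design effect introduced by clinic-level randomization will be addressed using a robust variance estimate". No patient characteristic is named, and neither are the randomisation strata, although Section 5.1.4 states: "Test sites will be stratified by region and size, then randomized to either arm at a 1:1 ratio (21 sites per trial arm").

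**Order of events.** Sites are randomised in the pre-implementation phase (Sections 5.1 and 5.1.4). Section 5.1.6 places the common SNaP training before "notifying the sites of their SA/TA allocation", and then adds that "TA implementation teams will subsequently visit each TA site in the region to conduct trainings on site-specific implementation strategies". Recruitment comes later, under Section 5.2: "Each site will consent PWID with a positive confirmatory test at the post-test counseling visit who are willing to allow medical chart review". The only masking described is that of the raters of navigation forms and recordings (Section 7.2.1).

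**Who enters.** Section 3.3 admits newly diagnosed people and a second group: "If previously diagnosed with HIV infection, then not currently on ART at the time of study enrollment (self-reported"). ART uptake is read from the clinic records of consenting PWID (Table 2), with those receiving SNaP as the denominator (Section 7.3.1).

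**Selection bias.** Section 8.3 recognises it as a difference between people who consent and people who do not. It offers reassurance on confidentiality and a count: "We will also track the numbers who decline to participate in the study". No comparison by arm and no adjusted or sensitivity analysis is attached.

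**The concern.** Randomising sites balances, in expectation, the sites and the populations they serve. It does not balance the people who are later identified, who agree to take part and who are counted, if those steps can depend on the arm. Here they happen after allocation is known, at sites where the tailored approach (TA) is meant to change how the site works.

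The two eligible groups may well differ in how readily they start ART: one has just received a diagnosis, while the other already knew of the infection and was not on treatment. If their proportions differ systematically by arm, the unadjusted difference mixes an implementation effect with a case-mix effect, in either direction. The robust variance corrects the standard error for clustering. It does nothing about a shift in the estimate itself.

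At stake is the primary effectiveness outcome, and with it the primary cost-effectiveness ratio, whose denominator is the difference in ART uptake (Section 2.1), and the DALY model built on that ratio (Section 8.2.2).

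**Working it through.** **1. The plan's own figures (Section 8.1.2).** Inputs: 6200 PWID, 42 sites, ICC 0.01 to 0.05, two-sided alpha 0.05. Mean cluster size m = 6200/42 = 147.6. Design effect = 1 + (m - 1) x ICC, with equal cluster sizes:

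- ICC 0.01: 1 + 146.6 x 0.01 = 2.47 (plan: 2.5). Effective n per arm = 3100/2.47, about 1257. Power for 70% vs 64% is 89.3%.
- ICC 0.05: 1 + 146.6 x 0.05 = 8.33 (plan: 8.4). Effective n per arm = 3100/8.33, about 372. Power for 70% vs 60% is 81.7%.

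The stated power above 80% for 6- and 10-point differences is reproduced.

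**2. Bias of an unadjusted difference.** Suppose the arms truly have no different effect. Let uptake be p_N in newly and p_P in previously diagnosed people, and let the share newly diagnosed be s_TA and s_SA. Expected uptake in an arm is s x p_N + (1 - s) x p_P, so the spurious difference is (s_TA - s_SA) x (p_N - p_P).

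The documents give none of these four quantities. All values below are assumptions. Cells are spurious differences in percentage points.

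| Imbalance in share newly diagnosed | Gap 10 | Gap 20 | Gap 30 | Gap 40 |
|---|---|---|---|---|
| 5 points | 0.5 | 1.0 | 1.5 | 2.0 |
| 10 points | 1.0 | 2.0 | 3.0 | 4.0 |
| 20 points | 2.0 | 4.0 | 6.0 | 8.0 |
| 30 points | 3.0 | 6.0 | 9.0 | 12.0 |

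Example: uptake 75% and 55%, share newly diagnosed 70% vs 50%. Then 0.70 x 75 + 0.30 x 55 = 69.0% and 0.50 x 75 + 0.50 x 55 = 65.0%, a spurious 4.0 points. To produce the whole 6-point planned effect takes a 30-point imbalance at a 20-point gap, or a 20-point imbalance at a 30-point gap.

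**3. Effect on the test.** Assume overall uptake of 65% and the design effects above. SE = sqrt(2 x 0.65 x 0.35 / effective n) = 1.90 points (ICC 0.01) or 3.50 points (ICC 0.05). Chance of two-sided p < 0.05 with no true effect:

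| Bias | ICC 0.01 | ICC 0.05 |
|---|---|---|
| 0 | 5% | 5% |
| 2 points | 18% | 9% |
| 4 points | 56% | 21% |
| 6 points | 88% | 40% |

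**4. Does adjustment also buy precision?** Assume uptake 75% and 50% with a 60/40 mix (65% overall). Diagnosis status then explains 0.6 x 0.4 x 0.25^2 / (0.65 x 0.35) = 0.0150/0.2275 = 6.6% of patient-level variance. But with m = 148 the patient-level part is only about 40% (ICC 0.01) or 11% (ICC 0.05) of the variance of a site mean. The total variance falls by about 2.6% or 0.8%, and the SE by about 1.3% or 0.4%. Precision is no argument for adjustment here, unless the mix also varies between sites, which the documents do not show.

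**5. Is the covariate available?** Section 5.5.1.1 lists consent and a bar-code sticker as the enrolment procedures for the approximately 5000 people outside the subsample, and Appendix I marks no questionnaire for them. Staff must consider diagnosis history to apply Section 3.3, but no passage says that it, or exact age, is stored as data for everyone.

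**The case against.** The plan leaves recruiting staff less discretion than the bare sequence suggests. Section 3.5.1 says everyone eligible who presents will be approached. Injecting history comes from routine site data (Section 5.2). Seek strategies are taught at the regional training with no arm-specific version (Section 5.1.6). SNaP is routine care offered whether or not a person joins (Sections 5.5 and 5.5.1.1), and the routine log counts all PWID diagnosed (Section 5.5). Section 9.3 describes scripted recruitment. All of this stands and lowers the risk. It does not settle who presents or who agrees, TA support continues through monthly calls (Section 4.2.2), and none of these measures is tied to a comparison of case mix by arm.

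A second objection is that TA may legitimately change who is reached, so adjustment could remove part of the pragmatic contrast. This also has force. The conceptual framework (Section 1.3) runs TA's effect through fidelity, penetration and acceptability, and penetration is a separate outcome (Section 7.2.2), so a shift in diagnosis mix is not the stated mechanism. Still, the two estimates answer different questions if TA changes the mix, which is a reason to report both.

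Third, adjustment handles only measured mix. It does not cure the receiving-SNaP denominator, and diagnosis status recorded by the same unmasked sites could itself be affected by arm. Both limits stand.

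**Conclusion.** The gap is real: a plan followed exactly as written would leave any arm difference in diagnosis mix inside the primary estimate, with nothing prespecified to detect or correct it. Its size cannot be estimated from the documents. The 0.5 to 12 points, set against detectable differences of 6 to 10, only shows that plausible-looking inputs run from negligible to as large as the planned effect; the upper end needs a large imbalance and a large uptake gap together.

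Four stronger readings are tempting and not supported. A reader might infer that staff will recruit selectively by arm; the documents state notification and no masking of recruiters, but nowhere predict differential recruitment. A reader might take one cell of the table as an estimate; every input is assumed, including which group has the higher uptake. A reader might expect adjustment to sharpen the comparison appreciably; step 4 shows a gain of about 1% of the SE or less. And a reader might think the remedy needs no new data; capture of diagnosis status outside the subsample is not shown. That the present model contains arm alone is itself inferred from the absence of any named covariate.

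**What to change.** In Section 8.2.1:

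- Prespecify a covariate-adjusted risk difference for ART uptake, standardised from a logistic model with site-clustered variance. This keeps the difference scale and avoids the convergence trouble of an identity-link binomial model with covariates.
- Adjust for newly versus previously diagnosed status, as determined when the inclusion criteria are applied, and for the randomisation strata region and size. Add age only if it is recorded for everyone.
- Report the unadjusted difference alongside. State which of the two is primary, and that they will differ if TA changes who is reached.
- Tabulate diagnosis status and consent rate by arm, and extend the decliner count in Section 8.3 to be reported by arm.

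In the enrolment procedures, record diagnosis status at screening for every enrollee, and confirm that it is captured for those outside the subsample.

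Cost: SAP wording, one extra analysis step and possibly one screening field. For anyone already enrolled without that field, the sponsor would need to establish whether the status can be recovered. The SAP should say plainly that adjustment covers measured case mix only and leaves the receiving-SNaP denominator as a separate limitation.

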### **8.2.3 High and Low Performing and Sustaining Site Characterization- Analyses (Aim 3)**

**Aim 3 - Qualitative data analyses:** All qualitative interviews will be audiotaped, transcribed, translated, coded and computerized for analysis using Atlas.ti v.8 software. Analysis will begin as data are collected so that topics for further exploration can be incorporated into ongoing fieldwork. Qualitative data analysis consists of the search for patterns in data and conceptualizing ideas that help explain the presence of those patterns. Textual data analysis will involve five steps: 1) reading for content; 2) deductive and inductive coding; 3) data display to identify emerging themes; 4) data reduction; and 5) interpretation. Memos will be written for each code. Codes will be refined during the process of analysis. Responses of navigators and counselors, test site staff, and test site directors will be compared within and across the staff groups and within and across high and low performing and sustaining sites. For example, we will compare navigator and counselors' attitudes around implementing SNaP, including PWID-related stigma, competing job responsibilities at the site, perceived effectiveness of SNaP, and perceived status/value of being navigators and counselors, by high and low performing sites to understand if and how these attitudes may ultimately affect site performance.

**Aim 3 - Quantitative data analyses:** The site characteristics will be assessed with exploratory analyses to examine associations with high and low performing and sustaining clinics. Site is the unit of analysis. Given the small sample size, we will assess each site measure separately. We will use a generalized linear model with a logit link and binomial error distribution to assess the dichotomous outcome of high or low performance and sustainment. Individual implementation or demographic measures will be included as an explanatory variable, with an indicator variable for study arm, and an interaction term (assessed with  $\alpha=0.10$ ). The interaction term will aid in interpreting whether a specific characteristic modified the effect of the implementation strategy. Two sets of models will be constructed: baseline measures only and change from baseline to evaluation.

**Data triangulation:** IDI and quantitative data will be triangulated to understand SNaP

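### The ART-uptake analysis leaves its robust variance unspecified and omits the randomisation strata; on the plainest reading, with 42 very unequal sites, the nominal 5% test rejects about 7% to 12% of the time

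*Combined protocol and SAP*

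**What the plan says.** Section 5.1.4 sets the allocation: "Test sites will be stratified by region and size, then randomized to either arm at a 1:1 ratio", giving 21 sites per arm, and "Randomization will be blocked within strata to ensure equal distribution by arm".

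Section 8.2.1 is the whole Aim 1 analysis plan. It compares arms by intention to treat with identity-link generalised linear models, Gaussian for means and binomial for proportions. For patient-level outcomes it adds only that "the design effect introduced by clinic-level randomization will be addressed using a robust variance estimate". Region and size are not mentioned, and neither are the working correlation, the form of the sandwich estimator, a small-sample correction, degrees of freedom or a reference distribution. No other section supplies them.

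Section 8.1.2 gives two-tailed α = 0.05, about 6200 patients, site sizes from 7 to 764 with a mean near 148, and "we estimate that the intra-cluster correlation coefficient may range from 0.01-0.05". It claims more than 80% power for 70% vs 60% uptake at the upper ICC and for 70% vs 64% at the lower.

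**The concern.** A sandwich variance relies on many clusters of broadly similar influence. Here there are 42, and one may hold 764/6200 = 12% of the patients. Without a correction the standard error tends to be too small and the test rejects too often.

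Leaving out the strata works the other way. Blocking balances the arms on region and size. If these predict uptake, a variance that ignores them is too large and the test loses power.

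The sentence in section 8.2.1 covers analyses that behave quite differently, and the choice among them could be made after the data are seen. What is at stake is the error rate of the primary effectiveness comparison.

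**Working it through.** **1. The plan's own figures.** With design effect DE = 1 + (m − 1)·ICC and m = 148:
- ICC 0.01: 1 + 147 × 0.01 = 2.47 (stated 2.5)
- ICC 0.05: 1 + 147 × 0.05 = 8.35 (stated 8.4)

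Effective size per arm is n = 3100/DE. Power is Φ{[δ − 1.96·√(2p̄(1 − p̄)/n)] / √[(p₁(1 − p₁) + p₂(1 − p₂))/n]}.
- 70% vs 60%, ICC 0.05: n = 371; (0.10 − 1.96 × 0.0350)/0.0348 = 0.90; power 81.6%
- 70% vs 64%, ICC 0.01: n = 1255; (0.06 − 1.96 × 0.0188)/0.0187 = 1.24; power 89.2%

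Both agree with the stated figure of more than 80%. The calculation treats all sites as the mean size and uses a normal reference.

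**2. Least possible size variation.** Given 42 sites, a total of 6200, a minimum of 7 and a maximum of 764, the spread is smallest when the other 40 sites are equal: (6200 − 771)/40 = 135.7 each. The standard deviation is then 98.2, and the CV is 98.2/148 = 0.66. Any real distribution with that range and mean varies at least this much.

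Even here, at ICC 0.05, independence weighting has DE = Σn(1 + (n − 1)·ICC)/6200 = 11.6. The effective total is 6200/11.6 = 534, against 6200/8.35 = 743 in the plan. Exchangeable weights, Σn/(1 + (n − 1)·ICC), recover 727.

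**3. Type I error by simulation.**
- From the protocol: 42 sites, sizes 7 to 764, total about 6200, ICC 0.01 and 0.05, blocked allocation within region and size, 21 per arm.
- Assumed: uptake 65% in both arms; size CV 0.66 to 1.3; 3 or 5 regions by 2 size groups; normal site effects; strata explaining 0% or 30% of between-site variance.
- Method: 10,000 null trials per setting, plus 6,000 per setting with unequal regions. Site proportions were fitted with an identity link, weighted by n (independence) or by n/(1 + (n − 1)·ICC) (exchangeable).

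| Analysis, nominal 5% | Strata explain 0% | Strata explain 30% |
|---|---|---|
| No strata, independence, plain sandwich, z | 7.0%–11.5% | 4.5%–10.5% |
| No strata, independence, G/(G−1) factor, t on 40 df | 5.8%–10.1% | 3.6%–9.1% |
| No strata, exchangeable, plain sandwich, z | 5.8%–7.1% | 3.2%–5.7% |
| No strata, exchangeable, G/(G−1) factor, t on 40 df | 4.9%–6.1% | 2.5%–4.7% |

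In the independence rows at 0%, the low end is at CV 0.66 and the high end at CV 1.3. Separately coded checks gave 8.4% to 11.9% for the first cell (lognormal-shaped sizes, CV 0.94 and 1.27, 3,000 trials per setting) and up to 6.3% for the exchangeable t test.

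**4. With stratum terms** (ranges also cover strata explaining 60%):
- Uncorrected sandwich, z: 8.2%–17.3% under independence, 6.8%–9.7% exchangeable.
- Kauermann-Carroll variance, t on sites minus parameters: 4.9%–8.6% under independence, 4.4%–5.9% exchangeable.

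A separate run of the last analysis reached 6.1% to 6.4% at CV 1.3 and ICC 0.01. With 2,500 trials, the Monte Carlo standard error is √(0.06 × 0.94/2500), about 0.5 points.

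**5. Power of that last analysis**, 70% vs 60%, ICC 0.05, strata not prognostic: 70%–79%. The exchangeable t test without strata has 72%–81%.

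**The case against.** The strongest reply is that section 8.2.1 does not commit to independence or to an uncorrected sandwich. An exchangeable fit with a t reference fits its wording and is close to nominal or conservative. Where the error falls below 5% the test is still valid and only power is lost. The size distribution, the number of strata and their prognostic strength are also not in the documents, so no single error rate can be assigned to the plan. All of this stands. It does not remove the problem, because the plan equally allows the independence analysis, and that one is inflated at the smallest possible size variation when the strata are not prognostic.

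A reader might infer more than the documents support:
- **That the stratum levels are undefined.** Figure 1, captioned as the randomisation scheme, is not reproduced in the text reviewed and may show them. Sections 3.1 (five areas) and 5.1.6 (three training regions) also suggest candidates.
- **That the sponsor concedes 42 sites are too few.** The remark in section 8.2.3, "Given the small sample size, we will assess each site measure separately", explains why exploratory site-level models take one measure at a time. It says nothing about variance estimation in Aim 1.
- **That the fidelity comparison is invalid.** It is analysed by site, so no sandwich is needed. Omitting strata there costs efficiency only.

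**Conclusion.** The concern holds for ART uptake and the other patient-level outcomes. On the plainest reading, type I error is about 7% to 12% at nominal 5% when the strata are not prognostic. About 7% to 8% requires only the stated size range and mean; the upper end needs a CV of about 1.3, an assumption. If the strata explain 30% of between-site variance, also an assumption, the same reading gives 4.5% to 10.5%.

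The exchangeable analysis with a t reference gives about 5% to 6.5% if the strata are not prognostic and about 2.5% to 5% at 30%. It would be wrong to pool the lowest and highest of these figures into one error range for the trial, since they belong to different estimators under different assumptions.

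This should be settled before analysis. It does not show that the trial's result would be wrong.

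**What to change.** In section 8.2.1, for ART uptake and other patient-level outcomes, pre-specify one analysis: an identity-link model with the region and size strata used in the allocation, exchangeable working correlation, Kauermann-Carroll corrected variance, and a t reference on sites minus model parameters. Simulated error is about 4.4% to 6%. If the binomial fit does not converge, use a Gaussian working variance with the same correction. The simulations, which fit weighted site proportions, are closest to that fallback. Do not add stratum terms to an uncorrected sandwich (about 7% to 17%).

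Recheck and restate the power in section 8.1.2, allowing for unequal site sizes and the t reference: the claim of more than 80% for 70% vs 60% at ICC 0.05 becomes roughly 70% to 79% if the strata are not prognostic.

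The cost is a few lines of text and code and 3 to 5 degrees of freedom (stratum levels assumed). Compared with the unadjusted exchangeable t test, power falls 1 to 3 points if the strata are not prognostic. If they explain 30%, it rises 5 to 7 points at ICC 0.05 and 2 to 3 at ICC 0.01. The estimate becomes more site-averaged if uptake depends on site size, so the trial team should confirm that this is the difference it wants.
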